## **8.2 Severity Grading**

The Investigator will grade all AE for severity. AE listed in the Guidance for Industry, Toxicity Grading Scale for Healthy Adult and Adolescent Volunteers Enrolled in Preventive Vaccine Clinical Trials ([FDA, 2007](#)) will be graded according to the criteria in the table. AE not listed in the Toxicity Grading Scale will be graded as follows:

- Mild (Grade 1): No interference with activity
- Moderate (Grade 2): Some interference with activity
- Severe (Grade 3): Significant; prevents daily activity
- Potentially Life-Threatening (Grade 4): ER visit or hospitalization

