## Stage 2:

- 1 SAE assessed as at least possibly related to study vaccine
- 1 subject with a Grade 4 (potentially life threatening) AE assessed as at least possibly related to study vaccine
- 2 subjects with the same or similar Grade 3 (severe) unsolicited AE assessed as at least possibly related to study vaccine other than solicited events
- Thirteen (13) subjects with the same or similar Grade 3 (severe) solicited AE
- Any concern from the Investigator or study team that warrants a study halt

The appropriate regulatory authority will be informed in writing when either of the following occurs:

- Study dosing is stopped.
- DMC has decided to resume or discontinue study activities.

Enrollment may be resumed following review of available safety data by the Sponsor.

Vaxcyte's clinical safety team will refer to the VAX31-101 Safety Medical Monitoring Plan for detailed procedures on stopping rule reporting and safety oversight for the study.

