### **10.6.3 Unsolicited Adverse Events**

All the unsolicited AE occurring during the study will be recorded, regardless of their assessment of relatedness by the Investigator.

The original verbatim terms used by Investigators to identify AE will be mapped to preferred terms using the MedDRA dictionary. The unsolicited AE will then be grouped by MedDRA preferred terms into frequency tables according to system organ class (SOC). All reported AE, as well as AE judged by the Investigator as at least possibly related to study vaccine, will be summarized by treatment group, according to SOC and preferred term within SOC. When an unsolicited AE occurs more than once for a subject, the maximum severity reported and strongest reported relationship to the treatment group will be counted.

Only TEAE will be summarized as defined in Section 8.1.1. The selection of unsolicited AE and their assignment to time intervals will be done by day of onset and not by days ongoing/persisting.

Unsolicited AE will be summarized by alphabetic SOC and preferred term as follows:

- Any unsolicited TEAE
- Possibly or probably related unsolicited TEAE
- SAE
- Possibly or probably related SAE
- NOCI
- MAAE
- Unsolicited TEAE leading to withdrawal
- Any AE leading to death

Listings of all TEAE will be provided by subject.

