6.5.1.2. Unsolicited Adverse Events

An unsolicited AE is an AE that is spontaneously reported by the subject or discovered by the Investigator. SAEs, NOCIs and MAAEs would be recorded as part of the collection of unsolicited AEs as specified in the visit procedures. Unsolicited AEs are collected separately from solicited AEs.

Solicited AEs continuing beyond 7 days will be identified using rules given in Section 5.2. They will not be presented in the summaries of unsolicited Adverse Events, but only in a Listing.

The definition of a treatment emergent AE (TEAE) is an event that occurs after vaccination and within the 30 days after vaccination (i.e., excluding those after a subject has given informed consent, but before vaccination):

- Onset (days) = Start date of AE – Date of Study Vaccine Administration + 1
- An AE is a TEAE if Onset \geq 1 and Onset \leq 30 and is not a continuing solicited AE

Adverse events are summarized by subject, therefore, in any tabulation, a subject contributes only once to the count for a given adverse event (SOC or preferred term).

Unsolicited AEs will be coded using the Medical Dictionary for Regulatory Activities (MedDRA) and will be summarized by decreasing frequency of SOC and preferred term within SOC in the control group, as follows:

- Unsolicited TEAEs
- Possibly or probably related unsolicited TEAEs
- Unsolicited TEAEs leading to study withdrawal

- SAEs
- Possibly or probably related SAEs
- NOCIs
- Possibly or probably related NOCIs
- MAAEs
- Possibly or probably related MAAEs
- AEs leading to death (only presented on the Safety Population overall)

Following summaries will be presented on the Safety Population overall only by decreasing frequency of PT, with an additional column “VAX-31” combining all subjects vaccinated with any dose of VAX-31:

- Unsolicited TEAEs
- Possibly or probably related unsolicited TEAEs

Following by-subject Listings will be provided:

- Pre-vaccination AEs (non-emergent)
- All unsolicited TEAEs
- All Serious post-vaccination AEs, NOCIs and MAAEs

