7. CHANGES TO PLANNED ANALYSES

There is no change between the protocol-defined statistical analyses and those presented in this statistical plan.

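### Protocol 10.6.3 counts the maximum severity of a repeated unsolicited AE, but no planned table shows unsolicited AEs by severity, so some Grade 3 events cannot be told from Grade 1 events by arm

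*SAP*

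**What the plan says.** Severity will be available for every event. Protocol 8.2 states "The Investigator will grade all AE for severity", on a four-level scale, and Protocol 8.5.2 lists severity among the items documented for each AE.

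Protocol 10.6.3 then says that when an unsolicited AE recurs in a subject, "the maximum severity reported and strongest reported relationship to the treatment group will be counted". The list of outputs in the same section opens with "Unsolicited AE will be summarized by alphabetic SOC and preferred term as follows" and has eight entries. None is by grade.

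SAP 6.5.1.2 says that coded unsolicited AEs "will be summarized by decreasing frequency of SOC and preferred term within SOC in the control group, as follows". It names ten event classes and adds two preferred-term tables with a pooled VAX-31 column. Its counting rule is one count per subject per SOC or preferred term. SAP 6.5.1.3 adds two summaries, covering solicited events that last beyond 7 days, alone and combined with unsolicited TEAEs. The only maximum-severity derivation is in SAP 6.5.1.1, for solicited AEs. SAP 7 states: "There is no change between the protocol-defined statistical analyses and those presented in this statistical plan".

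**The concern.** A maximum-severity rule has an effect only if some table sorts subjects by severity. Where each subject counts once per preferred term, the rule changes nothing. As written, it has no table to act on.

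Comparing the safety of VAX-31 with that of PCV20 is a primary objective, and this is a dose-finding study with three dose levels. If a higher dose made events more severe without changing how many subjects had one, the TEAE and related-TEAE tables would not show it. The protocol itself treats severe unsolicited events as relevant to decisions: one Stage 2 stopping criterion is "2 subjects with the same or similar Grade 3 (severe) unsolicited AE assessed as at least possibly related to study vaccine". Solicited AEs get maximum-severity tables overall and by day. Unsolicited AEs get none.

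**Working it through.** The point rests on comparing texts. The arithmetic only illustrates scale.

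**1. Where severity of unsolicited AEs could appear by arm**

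| Planned output | What it can show about severity |
|---|---|
| Unsolicited TEAEs and related TEAEs, by SOC/PT and by PT (SAP 6.5.1.2) | Nothing |
| Prolonged solicited events, alone and combined with unsolicited TEAEs (SAP 6.5.1.3) | Nothing |
| SAE, related SAE, AEs leading to death | Seriousness, which overlaps with high grades |
| MAAE, related MAAE | Medical attention at any grade, through 6 months |
| NOCI, related NOCI | New chronic illness at any grade |
| TEAEs leading to withdrawal | Consequence at any grade |
| By-subject listings | Possibly the grade, but not a summary by arm |

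**2. Which events are hidden.** For AEs outside the published toxicity scale, Protocol 8.2 gives "Potentially Life-Threatening (Grade 4): ER visit or hospitalization". An unplanned emergency visit also meets the MAAE definition in Protocol 8.1.1, so most such Grade 4 events would surface in the MAAE or SAE tables. Grade 3 on the same scale means that daily activity is prevented, which need not involve a doctor. A Grade 3 event that is non-serious, not medically attended, not a new chronic illness and without withdrawal appears only in the tables in the first two rows, where it looks the same as a Grade 1 event.

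**3. Month 1.** SAP 2.6 excludes individual listings from the Month 1 delivery, so the specified outputs give readers of that analysis no grades for unsolicited AEs.

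**4. Scale.** Inputs: 250 subjects per arm (Protocol 10.3) and a 12.3% TEAE rate within 1 month in the VAX-24 groups (Protocol 2.1). Assumption: the same rate holds in each arm here.

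- Subjects per arm with any unsolicited TEAE: 250 × 0.123 = 30.75, about 31. This counts any grade. The documents give no Grade 3 rate, so under this assumption the number with Grade 3 or higher could be anywhere from 0 to about 31.
- Age 65 and older, at the minimum of 200 with equal allocation: 200 / 4 = 50 per arm, and 50 × 0.123 = 6.15, about 6 subjects.

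**5. What a severity row would add.** Suppose two arms each have 31 of 250 subjects (12.4%) with a TEAE. The SAP's any-TEAE row reads 31 against 31 whatever the grades. With an assumed number of Grade 3 subjects in one arm and none in the other, Fisher's exact test (two-sided) gives:

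| Grade 3 subjects | Percent | p |
|---|---|---|
| 3 vs 0 | 1.2 vs 0 | 0.25 |
| 6 vs 0 | 2.4 vs 0 | 0.030 |
| 10 vs 0 | 4.0 vs 0 | 0.0018 |
| 15 vs 0 | 6.0 vs 0 | <0.001 |

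The severity splits are invented for illustration. The p-values only indicate how visible such a split would be; the plan specifies no safety tests.

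**The case against.** The best defence is that the protocol never promised a severity table. Its sentence is a conditional counting rule for repeats, and its eight listed outputs all reappear in the SAP, with related NOCI and related MAAE added. Where the protocol wants tables by maximum severity, in 10.6.2, it asks for them, and only for solicited AEs. This stands. The gap lies in both documents.

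It also limits four stronger readings that a reader might infer:

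- **That SAP 7 is a false declaration on this point.** No listed protocol table by severity was dropped. What was left out, without being declared, is a counting rule. The sort order also differs (alphabetic in the protocol, decreasing control-group frequency in the SAP), but that is presentation only.
- **That the SAP kept the relationship half of the rule and removed the severity half.** The SAP does define a maximum relationship for unsolicited AEs, but in 6.5.1.1, among the solicited endpoints. The word may be a slip, so selective omission cannot be shown.
- **That arms differing in severity would look the same throughout.** This holds for the TEAE and related-TEAE tables. The SAE, MAAE, withdrawal and death tables would reveal part of a difference.
- **That severe clusters would go unseen during vaccination.** The stopping criterion needs two subjects, a same or similar event and at least possible relatedness. It operates through the Medical Monitor and the DMC, not through SAP tables.

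Listings are planned for the final analysis, but they are not a comparison by arm. SAP 2.6 leaves the exact Month 1 output list to a separate document, which could add a severity table; the SAP does not require it. Part of Protocol 10.6.4 is blacked out, and nothing here is inferred from that.

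**Conclusion.** The point holds in a limited form. Every unsolicited AE is graded and the protocol has a maximum-severity rule, yet following the SAP exactly produces no by-arm summary of unsolicited AEs by grade. What is lost is mainly the visibility of Grade 3 TEAEs that are non-serious, not medically attended and do not lead to withdrawal.

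The primary endpoint, the percentage of subjects with an unsolicited AE within 1 month, has no severity component and is delivered as planned. The gap concerns how fully the safety comparison is reported.

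Its size cannot be stated. About 31 subjects per arm is the number with any unsolicited TEAE if the VAX-24 rate carries over to every arm, including PCV20. It should not be read as a count of severe events.

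**What to change.** In SAP 6.5.1.2:

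1. Extend the maximum-severity derivation to unsolicited AEs, per subject, SOC and preferred term. State how a missing grade is handled and, for the related table, whether the maximum is taken over related occurrences only.
2. Add two tables for the Overall (50+) group: unsolicited TEAEs and related unsolicited TEAEs, by SOC and preferred term and by maximum severity, each with a row for any Grade 3 or higher by arm.
3. In the 50-59, 60+ and 65+ groups, give that summary row only. With about 6 TEAE subjects per arm in the smallest group under the assumed rate, a full breakdown by term and grade would be almost empty.
4. Include the Overall tables in the Month 1 output list, subject to the unblinding review in SAP 2.6.

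If the sponsor prefers not to tabulate severity, SAP 7 should say that the Protocol 10.6.3 rule is not used, and why.

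The cost is one derived variable and a few sparse tables. No new data and no protocol amendment are needed.

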6.5.1.3. Combined Solicited and Unsolicited Adverse Events

Solicited AEs continuing beyond 7 days will be recorded by the sites and flagged using rules given in Section 5.2. They will be coded by MedDRA and following summary by decreasing frequency of SOC and preferred term within SOC will be provided:

- Solicited TEAEs continuing beyond 7 days
- Combined solicited TEAEs continuing beyond 7 days and unsolicited TEAEs

Following by-subject Listings will be provided:

- All solicited TEAEs continuing beyond 7 days

6.5.2. Laboratory Data

- A summary describing pregnancy tests results at Baseline will be presented on the overall population only. The list of Baseline test results to be described is given in *Table 2*.

Table 2 Baseline Laboratory Tests

Panel	Sample	Parameter
Urinalysis	Urine	Pregnancy (urine)

- The lists of laboratory parameters analyzed can be found in *Table 3*. Only the parameters in this table will be presented in the following summaries:
 - The actual value and change from Baseline to Month 1 will be summarized for each clinical laboratory parameter, including hematology, clinical chemistry, and urinalysis. For subjects discontinuing early before Month 1, the value at Early Study Discontinuation will be presented in Listings only.
 - A shift table from Baseline to Month 1 presenting abnormal values for each parameter will also be presented. For subjects discontinuing early before Month 1, the abnormal values at Early Study Discontinuation will be used instead of Month 1.

Clinical laboratory values will be expressed using conventional international system of units (SI). In the event of repeat values, the last non-missing value per study day/time will be used. Clinically significant out-of-range lab results will be reported as adverse events by Investigators. Clinical significance will therefore not be reported in the laboratory outputs.

Table 3 Laboratory Parameters Collected and Summarized in Tables

Panel	Sample	Parameter
Hematology	Blood	Eosinophils (absolute)
Hematology	Blood	Hemoglobin
Hematology	Blood	Neutrophils (absolute)
Hematology	Blood	Platelet count
Hematology	Blood	White blood cell count (absolute)
Chemistry	Serum	Albumin
Chemistry	Serum	Alkaline phosphatase
Chemistry	Serum	Alanine aminotransferase (ALT)
Chemistry	Serum	Aspartate aminotransferase (AST)
Chemistry	Serum	Bicarbonate
Chemistry	Serum	Bilirubin (Total)
Chemistry	Serum	Bilirubin (Direct)
Chemistry	Serum	Blood urea nitrogen (BUN)
Chemistry	Serum	Calcium
Chemistry	Serum	Chloride
Chemistry	Serum	Cholesterol
Chemistry	Serum	Creatinine
Chemistry	Serum	Gamma-glutamyl transferase (GGT)
Chemistry	Serum	Glucose (random)
Chemistry	Serum	Lactate dehydrogenase (LDH)

Chemistry	Serum	Phosphorus
Chemistry	Serum	Potassium
Chemistry	Serum	Protein total
Chemistry	Serum	Sodium
Chemistry	Serum	Triglycerides
Chemistry	Serum	Uric acid
Urinalysis	Urine	Bilirubin
Urinalysis	Urine	Blood
Urinalysis	Urine	Glucose
Urinalysis	Urine	Ketones
Urinalysis	Urine	Leucocyte Esterase
Urinalysis	Urine	Nitrite
Urinalysis	Urine	pH
Urinalysis	Urine	Protein (Total)
Urinalysis	Urine	Specific Gravity (SG)
Urinalysis	Urine	Urobilinogen

All laboratory data will be provided in data listings.

6.5.3. Vital Signs

The actual value and change from before study vaccine administration to after study vaccine administration will be summarized for each vital sign parameter: Systolic Blood Pressure, Diastolic Blood Pressure, Heart Rate, Oral Temperature, Respiratory Rate. In case of multiple measurements on Day 1 before vaccination, the closest measure from the time of vaccination will be used. In case of multiple measurements on Day 1 after vaccination, the closest measure from the time of vaccination will be used. Vital sign measurements will be presented in by-subject data listings.

6.6. Immunogenicity Evaluations

All Immunogenicity summaries to be produced by treatment group, for the following:

Population: IEP, EXP

Subgroups: Overall (50+), 50-59, 60+, 65+

All immunogenicity data will be provided by-subject data listings on the Exposed Population.

6.6.1. GMT/GMC, GMR and GMFR

To estimate the immunogenicity response 1 month after vaccination, OPA titers (log10) and IgG concentrations (mcg/mL) measured at Month 1 visit will be logarithmically transformed for analysis and GMTs/GMCs will be computed with 95% CI for each assay using ANOVA and ANCOVA.

- First model in an ANOVA with log10-transformed concentrations/titers at Month 1 as the dependent variable and treatment group and study site as the fixed effects in the model.
- Second model in an ANCOVA with log10-transformed concentrations/titers at Month 1 as the dependent variable, treatment group and study site as the fixed effects and log10 baseline concentration/titer as the covariate

The least squares means, and their 95% CIs calculated based on the ANOVA and ANCOVA will be back transformed and reported as the group GMT and GMC values. The p-value for the mean difference between groups, calculated using the F-test from the ANOVA/ANCOVA model, will be reported as well.

Comparisons between relevant groups will be done using GMRs. They will be calculated using the estimated adjusted GMTs/GMCs measured at Month 1 visit for all 31 serotypes in VAX-31 (of those 20 in PCV20), and mean square error calculated from the ANOVA and ANCOVA models using contrast statements. The main comparison of interest will be the three VAX-31 dose level groups versus the PCV20 (20 serotypes) group. However, the three VAX-31 dose level groups will also be compared in a pairwise fashion on a serotype-by-serotype basis. No adjustment for multiplicity will be applied and missing data will not be imputed.

[figure not shown]
The analysis of GMFR at Month 1 relative to Day 1 will also be computed using similar models:

- First model in an ANOVA with log10-transformed fold ratio at Month 1 as dependent variable and treatment group and study site as the fixed effects in the model.
- Second model in an ANCOVA with log10-transformed fold ratio at Month 1 as dependent variable, treatment group and study site as the fixed effects and log10 baseline concentration/titer as the covariate

The least squares means, and their 95% CIs calculated based on the ANOVA and ANCOVA will be back transformed and reported as the group GMFR value. No comparison between groups will be made.

The following Figures will be provided on the IEP only:

- A reverse cumulative distribution curve of OPA titers on Day 1 and Month 1 by treatment groups for each serotype
- A reverse cumulative distribution curve of IgG concentrations on Day 1 and Month 1 by treatment groups for each serotype
- Bar Plot of OPA GMTs at Month 1 from ANOVA model by treatment group and serotype
- Bar Plot of IgG GMCs at Month 1 from ANOVA model by treatment group and serotype

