## **10. Statistical Analysis**

This Phase 1/2 study is designed to achieve both safety and immunogenicity objectives.

The primary objectives are to evaluate the safety of a single injection of VAX-31 at 3 dose levels and to compare the safety of VAX-31 to that of PCV20 administered to 4 groups:

- Subjects aged 50 to 59 years receiving PCV20
- Subjects aged 50 years and older receiving PCV20
- Subjects aged 60 years and older receiving PCV20
- Subjects aged 65 years and older receiving PCV20

The secondary immunogenicity objectives are to assess the induction of OPA and MSD antibody responses by VAX-31 at 3 dose levels compared to the 20 PCV20 serotypes (1, 3, 4, 5, 6A, 6B, 7F, 8, 9V, 10A, 11A, 12F, 14, 15B, 18C, 19A, 19F, 22F, 23F and 33F), as measured at 30 days after the injection (Month 1) and 11 non-PCV20 serotypes (2, 7C, 9N, 15A, 16F, 17F, 20B, 23A, 23B, 31 and 35B), as compared to the standard regulatory criteria for efficacy (e.g., lower bound of the 2-sided 95% CI for the geometric mean ratio GMR for a given serotype greater than 0.5 for noninferiority of shared serotypes and the lower bound of the 2-sided 95% CI for the geometric mean ratio GMR for a given serotype greater than 2.0 for superiority of the novel serotypes), measured at 30 days after the injection (Month 1) for subjects aged 50 to 59 years, 50 years and older, 60 years and older, and 65 years and older.

A statistical analysis plan (SAP) will be generated and approved prior to the interim analysis and treatment group unblinding for the primary safety and secondary immunogenicity endpoints through Month 1 visits. Individual treatment unblinding will occur after the data are cleaned

through the last Month 6 visits and final database lock. A single completed Clinical Study Report (CSR) will summarize safety and immunogenicity findings through Month 6 for all 1000 subjects.

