## **10.7 Immunogenicity Analysis**

### **10.7.1 Geometric Mean Titer, Geometric Mean Concentration, and Geometric Mean Titer Fold Rise**

Immunogenicity analyses will be performed by age group (50 to 59, 60 years and older, 65 years and older) and overall (50 years and older). Analyses will be performed for both OPA titers ( $\log_{10}$ ) and IgG titers (mcg/mL). All immunogenicity analyses will be based on the IEP and Exposed Population.

The Geometric Mean Titer (GMT) and Geometric Mean Concentration (GMC) will be analyzed via linear models. The primary model is an analysis of variance (ANOVA), with logarithmically-transformed titers ( $\log_{10}$ ) as the dependent variable and treatment group and study site as the fixed effects in the model. The results included in the main tables of the report will be based on this basic ANOVA model. As a secondary analysis, in order to remove the effect of baseline concentration on the GMT, an analysis of covariance (ANCOVA) will also be performed. The ANCOVA includes treatment group and study site as the fixed effects and  $\log_{10}$  baseline titer as the covariate in the model. The rationale for including baseline values as a covariate is that prior data have shown vaccine response is correlated with baseline antibody levels.

The least squares means and their 95% confidence intervals (CI) calculated based on the ANOVA and ANCOVA will be back transformed and reported as the group GMT and GMC values (adjusted for the mean baseline in the case of the ANCOVA). GMR will also be calculated from the ANCOVA and ANOVA models.

Comparisons between relevant groups will be based on the estimated adjusted GMT measured at Month 1 for 31 serotypes in VAX-31 (of those 20 in PCV20), and mean square error calculated from the basic ANOVA model using contrast statements. The analysis of GMFR relative to Day 1 will also be computed using similar models.

The main comparison of interest will be the 3 VAX-31 dose level groups vs the PCV20 (20 serotypes) group. However, the 3 VAX-31 dose level groups will also be compared in a pairwise fashion on a serotype-by-serotype basis. No adjustment for multiplicity will be applied, and missing data will not be imputed.

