2. STUDY DESIGN

2.1. Introduction

This Phase 1/2 parallel-group, randomized, 2-stage observer-blind study is to be conducted in 3 populations of healthy adults, aged 50 to 59, 60 to 64, and 65 years and older. Subjects will be randomly assigned in a 1:1:1:1 ratio to receive either VAX-31 at 1 of 3 dose levels or a single dose of PCV20, the active comparator.

In Stage 1 of the study, 64 subjects (16 for each VAX-31 dose group and 16 for the comparator group) 50 to 64 years of age will be enrolled initially. If the DMC agrees that the study may continue after reviewing data from Stage 1, approximately 736 additional adults aged 50 to 64 years as well as a minimum of 200 adults aged 65 years and older will be concurrently enrolled in Stage 2. Subjects will have screening procedures (physical examination, vital signs, urine pregnancy test for females of childbearing potential), and if eligible, will be enrolled into the study and receive VAX-31 or PCV20 on Day 1. All subjects will have a urine sample collected as well as blood samples drawn for immunogenicity analysis (OPA and IgG) and safety laboratory analysis at Day 1 (before vaccination) and Month 1 (30 days after vaccination). Solicited Adverse Events (AEs) will be collected for 7 days after vaccination and unsolicited safety information for 30 days after vaccination, with Serious Adverse Events (SAEs), New Onset of Chronic Illnesses (NOCIs), and Medically Attended Adverse Events (MAAEs) collected up to 6 months after vaccination.

A defined safety review of data (solicited and unsolicited AE and SAE) through 7 days after vaccination of the 64 subjects in Stage 1 will be conducted by an independent Data Monitoring Committee (DMC) before proceeding with Stage 2 of the study.

The schedule of assessments is in Appendix A, further details available in the study protocol.

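### One four-arm mean square error sets every GMR interval, although equal variance across arms is doubtful for the 11 serotypes that PCV20 lacks

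*SAP*

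**What the plan says.** For each serotype and assay, SAP 6.6.1 fits an ANOVA to log10 Month 1 values with "treatment group and study site as the fixed effects in the model", and an ANCOVA that adds the log10 baseline value. Group comparisons are GMRs whose precision comes from the "mean square error calculated from the ANOVA and ANCOVA models using contrast statements". Protocol 10.7.1 has the same approach for one model: "mean square error calculated from the basic ANOVA model using contrast statements". Treatment group has four levels ("Subjects will be randomly assigned in a 1:1:1:1 ratio"), so each fit yields one residual variance estimated over all four arms. The word pooled is not used, but no other reading fits the text.

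GMRs are planned "for all 31 serotypes in VAX-31 (of those 20 in PCV20"), and protocol section 10 lists the rest as "11 non-PCV20 serotypes (2, 7C, 9N, 15A, 16F, 17F, 20B, 23A, 23B, 31 and 35B"). Two families of contrasts share the variance:

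- VAX-31 against PCV20: "The main comparison of interest will be the three VAX-31 dose level groups versus the PCV20 (20 serotypes) group".
- Dose against dose: the VAX-31 groups "will also be compared in a pairwise fashion on a serotype-by-serotype basis".

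SAP 5.2 sets results below LLOQ to 0.5*LLOQ for GMTs, GMCs and GMRs. Protocol section 10 gives, as examples of regulatory criteria, a lower 95% bound of the GMR above 0.5 for shared serotypes and above 2.0 for the novel ones. The visible text has no arm-specific variance, robust standard error, check of the variance assumption or sensitivity analysis for it.

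**The concern.** A contrast between two arms should carry the variances of those two arms. A four-arm mean square error gives it the average of all four. With three VAX-31 arms and one PCV20 arm, three quarters of that average comes from VAX-31.

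For the 11 novel serotypes there is a design reason to doubt that the arms share a variance. The VAX-31 arms show a vaccine response. The PCV20 arm shows background antibody a month later, with any result below LLOQ moved to a single constant. If the spreads differ, the intervals are wrong in opposite directions for the two families. Equal allocation does not protect against this, because the variance is averaged over four arms and used for two. At stake are the precision of the dose-versus-dose comparisons in a dose-finding study and the lower bound that is compared with 2.0.

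**Working it through.** **No figure in the plan to reproduce on this point.** The documents state no SD, power or precision for the GMRs. Their one computed figure, the chance of seeing an event among 16 subjects, does reproduce (1 − 0.85^16 = 92.6%; 1 − 0.90^16 = 81.5%) but does not bear on this question.

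**Inputs.** Four equal arms: 250 each overall (protocol 10.3), and about 50 each in the 65+ group if its minimum of 200 splits equally. Two-sided 95% intervals. Assumed, because the documents are silent: the three VAX-31 arms share one SD, and r is the PCV20 SD divided by that SD, taken from 0.5 to 2.

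**Formulas**, with the VAX-31 SD set to 1 and n per arm:

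- Mean square error = (3 + r²)/4, so every contrast is given variance 2 × MSE/n = (1.5 + 0.5r²)/n.
- True variance: (1 + r²)/n for VAX-31 versus PCV20, and 2/n for dose versus dose.
- Used minus true: 0.5(1 − r²)/n and 0.5(r² − 1)/n. The signs are opposite, so for any r other than 1 exactly one family is too narrow.
- SE ratio (used/true): √[(3 + r²)/(2(1 + r²))] and √[(3 + r²)/4].
- Coverage = 2Φ(1.96 × ratio) − 1; one-sided error = 1 − Φ(1.96 × ratio).

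For example, at r = 0.5 the ratios are √(3.25/2.5) = 1.140 and √(3.25/4) = 0.901.

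| r | SE ratio, vs PCV20 | Coverage | One-sided error | SE ratio, dose vs dose | Coverage | One-sided error |
|---|---|---|---|---|---|---|
| 0.5 | 1.140 | 97.5% | 1.3% | 0.901 | 92.3% | 3.9% |
| 0.8 | 1.053 | 96.1% | 2.0% | 0.954 | 93.9% | 3.1% |
| 1 | 1.000 | 95.0% | 2.5% | 1.000 | 95.0% | 2.5% |
| 1.25 | 0.944 | 93.6% | 3.2% | 1.068 | 96.4% | 1.8% |
| 1.5 | 0.899 | 92.2% | 3.9% | 1.146 | 97.5% | 1.2% |
| 2 | 0.837 | 89.9% | 5.1% | 1.323 | 99.1% | 0.5% |

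Dose-versus-dose coverage cannot fall below 91.0% (r near 0). Coverage against PCV20 cannot fall below 83.4% (r very large).

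**Simulation.** A four-arm ANOVA with 25 sites, 8,000 runs per setting and 250 per arm gave coverage (vs PCV20 / dose vs dose) of 97.3% / 91.9% at r = 0.5, 92.2% / 97.8% at 1.5 and 90.1% / 99.0% at 2. Results at 50 per arm were nearly the same, so sample size is no remedy. Arm-specific variances brought coverage back to between 94.5% and 96.1% in every setting.

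**Effect on the 2.0 criterion**, with an assumed VAX-31 SD of 0.6 log10 and 250 per arm:

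- r = 1.5: lower bound is GMR × 0.758 as planned and GMR × 0.734 with the true variance. The conclusion changes only for an observed GMR between 2/0.758 = 2.64 and 2/0.734 = 2.72.
- r = 0.5: the factors are 0.804 and 0.826. The planned interval misses superiority for a GMR between 2/0.826 = 2.42 and 2/0.804 = 2.49.
- At 50 per arm and r = 1.5, the factors are 0.538 and 0.501, a band from 2/0.538 = 3.72 to 2/0.501 = 3.99.

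**The case against.** The strongest reply is that no defect has been shown. A common-variance ANOVA on log titers is coherent and fully specified, and no SD in the documents establishes that the arms differ or in which direction. That stands, and it is why the point is conditional. Below-limit values at one constant would tend to shrink the PCV20 spread; mixed pre-existing antibody could enlarge it.

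Two stronger readings are tempting, and the documents support neither. A reader might infer that superiority claims against 2.0 are too easily won, with error up to 5.1%. That needs a PCV20 SD well above the VAX-31 SD, whereas the below-limit rule points the other way, to a conservative bound. A reader might also infer that all GMR intervals are suspect. The reason given does not reach the 20 shared serotypes, where every arm receives antigen and which the SAP names as the main comparison.

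The consequence is also limited. SAP 3.3 lists GMR as exploratory, the contrasts are unadjusted for multiplicity, the 2.0 bound is given as an example, and no success threshold is visible for dose against dose. Protocol 10.7.2 has a further analysis of the novel serotypes, on 4-fold OPA rise, that does not use this variance. All this lowers the severity without making the intervals right. SAP 6.2.4 says there are no formal tests, but SAP 6.2.1 plans immunogenicity tests at the two-sided 0.05 level.

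Finally, a mixed model with arm-specific variances and 25 site effects may fail to converge if one arm sits near the floor. It may also let that arm dominate the site estimates and so move the point estimates. That stands and shapes the fix.

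**Conclusion.** The concern holds for the 11 non-PCV20 serotypes, and only conditionally. If the PCV20 SD is half the VAX-31 SD, dose-versus-dose intervals cover about 92% and the VAX-31 versus PCV20 bound is conservative. If it is 1.5 or 2 times as large, VAX-31 versus PCV20 intervals cover about 92% or 90%. For ratios between 0.8 and 1.25 the narrower family still covers about 94%. These figures assume near-equal arms and a common SD across the VAX-31 doses. The direction is not established, although the below-limit rule favors the first case. Severity is low: a cheap improvement that few individual conclusions will turn on.

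**What to change.** In SAP 6.6.1, for the 11 non-PCV20 serotypes, keep the planned ANOVA and ANCOVA point estimates and take the GMR confidence intervals from heteroscedasticity-consistent standard errors (HC3, for example). These leave the fit and site weighting unchanged. Arm-specific residual variances with Satterthwaite degrees of freedom are an alternative where that model converges; the simulated recovery of coverage was for arm-specific (Welch-type) variances, not for HC3. SAP section 7 now declares no change from the protocol, so the departure from protocol 10.7.1 should be recorded there before unblinding, which in practice means before the interim database lock for the Month 1 Analysis.

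The cost is a declared change and slightly wider intervals in the smallest subgroup, at about 50 per arm. If the variances prove equal, almost nothing is lost.
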